8.2 Efficacy Assessments

8.2.1 Average Daily Pain Score

The average daily pain score will be obtained using the daily, 24-hour recall, NRS pain data collected with the diary system. Since a mean is used in the calculation of the primary endpoint, it is not necessary to replace values missing on random intermittent days.

The baseline pain score will be defined as the average of the pain scores from the 7 days prior to the baseline visit. Pain scores must be recorded on at least 5 out of the 7 days immediately preceding the baseline visit in order for the subject to qualify for randomization.

The mean of the daily, subject self-reported, 24-hour recall, pain severity scores for the 7 days of each week will serve as the pain score for that study week. All available values will be used; if a subject has at least one value for the week, the week is non-missing. Because there is a -4 day and +7 day window around the scheduling of Visit 6 (Day 99), the study weeks will be anchored by the timing and completeness of their final study visit. Ideally, subjects appearing in-clinic on Day 99 (defining randomization as Day 1), would have last filled out their diary on Day 98; therefore, "Week 14" would include Days 92-98; the protocol-defined window allows visit 6 as early as Day 95, resulting in a nominal "Week 14" including Days 88-94. Likewise, subjects may appear in-clinic per protocol as late as Day 106, resulting in a "Week 14" interval running from Day 99-105.

Due to impacts from the COVID-19 pandemic, the criteria for calculating the Week 14 average will be marginally relaxed beyond the protocol-specified visit windows to allow for additional flexibility by permitting data collected during Week 13 to be used to calculate the Week 14 average: working backwards from Day 98, the first non-missing day (as early as Day 91) will serve as the LAST day of Week 14 for the purpose of anchoring and any non-missing values in the 6 days prior to that day will contribute to the average. If a subject does not have a non-missing value on/after Day 91, any available data from Day 85-91 will be averaged as Week 14 and Day 91 will serve as the anchor. Subjects without data on/after Day 85 will be missing for Week 14 and handled as described below. Specific examples of calculating the Week 14 pain score are described in [Appendix C](#).

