Each week prior to Week 14 will be based on 7-day intervals; depending on the interval selected for "Week 14", this will result in Week 1 having less than 7 days or some "extra" days prior to Week 1. Extra days will be dropped and not included in the analysis; in the case of less than 7 days, the available days will be averaged, as long as there are non-missing values. The earliest

day included in the Week 1 average will be the data entered the day after randomization (covering roughly the 24 hours following their first dose of study drug).

For subjects who withdraw from the study early, that do not have a final study visit or complete the study but do not have data in the 7 days preceding their last visit, the last day of diary data (at or prior to Day 106) will serve as the anchor point for dividing the available data into weeks. First, the nearest nominal end day for a weekly period is identified and this week will be the assigned the data from the 7 days immediately preceding the anchor date. For example, if a subject early terminates on study Day 24, the Week 3 (nominally ending on day 21) average will be based on the 7 days prior to Day 24 (Days 17-23). Lost to follow-up subjects that continue to fill out the diary into Week 14 and beyond will have non-missing values for the Week 14 timepoint for diary outcomes. Day 106 will be the last allowable day to be included in the average.

| Week | Nominal Study Day Intervals |
|----------------------|-----------------------------|
| Baseline | Day -7 to -1 |
| Day of Randomization | Day 1 |
| Week 1 | Day 2 to 7 |
| Week 2 | Day 8 to 14 |
| Week 3 | Day 15 to 21 |
| Week 4 | Day 22 to 28 |
| Week 5 | Day 29 to 35 |
| Week 6 | Day 36 to 42 |
| Week 7 | Day 43 to 49 |
| Week 8 | Day 50 to 56 |
| Week 9 | Day 57 to 63 |
| Week 10 | Day 64 to 70 |
| Week 11 | Day 71 to 77 |
| Week 12 | Day 78 to 84 |
| Week 13 | Day 85 to 91 |
| Week 14 | Day 92 to 98 |

Change from baseline will be defined as the pain score at each week minus the baseline pain score (with baseline and weekly pain scores derived as described above). Thus, negative changes will denote lesser pain and larger negative values will denote greater improvement.

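### The early-withdrawal diary rule in SAP 8.2.1 anchors on the last diary day but averages the 7 days before it, so the last entry is left out, against the rest of the section

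*SAP*

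**What the plan says.** SAP 8.2.1 has a separate rule for three groups: early withdrawals, subjects with no final visit, and completers with no diary data in the 7 days before their last visit.

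- **Anchor:** "the last day of diary data (at or prior to Day 106) will serve as the anchor point for dividing the available data into weeks".
- **Week label:** "First, the nearest nominal end day for a weekly period is identified".
- **Days averaged:** "this week will be the assigned the data from the 7 days immediately preceding the anchor date".
- **Example:** for early termination on Day 24, the Week 3 "average will be based on the 7 days prior to Day 24 (Days 17-23").
- **Upper limit:** "Day 106 will be the last allowable day to be included in the average".

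Other text bears on the same derivation:

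- Earlier in 8.2.1, the relaxed Week 14 rule works back from Day 98. The first day with a score, down to Day 91, is the last day of Week 14, and the 6 days before it also count. Failing that, any scores from Days 85–91 are used.
- Section 8.2.1 also says that "if a subject has at least one value for the week, the week is non-missing", and that a subject seen on Day 99 ideally "would have last filled out their diary on Day 98".
- In Appendix C, every row that states an end day finishes on the last diary day, except the late row: a last score on Day 106 or later gives Days 99–105.
- Section 8.2.2 applies the pain derivation to diary sleep quality. Section 8.1.3 uses the weekly scores as imputation covariates.

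**The concern.** If the anchor is the last day with an entry, and the week is the 7 days before the anchor, the last entry is never averaged. It is the entry nearest to the decision to leave.

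The rule fixes the last observed week and, by counting back, the earlier ones. For a diary that ends before Day 85 it is the only rule available. Those weekly means are predictors when the subject's later weeks are imputed, for pain and for the diary sleep endpoint. One programmer could follow the sentence and another the example, and they would build different analysis datasets with each able to cite the SAP.

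**Working it through.** **Inputs.** All day limits come from SAP 8.2.1 and Appendix C. L is the last diary day. The nominal week ends are Days 7, 14, …, 98, and the earliest usable day is Day 2. The documents give no day-to-day SD or expected withdrawal rate that could be used here, so both are assumed below.

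**1. The worked example and other fixed points.** Literal window: L−7 to L−1. Window ending on the last entry: L−6 to L.

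| L | Week | Literal | Ending on L | Stated elsewhere in the SAP |
|---|---|---|---|---|
| 23 | 3 | 16–22 | 17–23 | Example, termination Day 24: 17–23 |
| 24 | 3 | 17–23 | 18–24 | Same example, if an entry was made on Day 24: 17–23 |
| 95 | 14 | 88–94 | 89–95 | Week 14 rule and Appendix C: 89–95 |
| 98 | 14 | 91–97 | 92–98 | Week 14 rule and Appendix C: 92–98 |
| 105 | 14 | 98–104 | 99–105 | Appendix C: 99–105 |
| 106 | 14 | 99–105 | 100–106 | Day 106 sentence: Day 106 may be included; Appendix C late row: 99–105 |

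The example states no last diary day. By the visit convention (visit Day 99, last entry Day 98) it would be Day 23. The literal rule then gives Days 16–22 and does not reproduce Days 17–23; the inclusive window does. If there was an entry on Day 24, rule and example agree, but both discard that entry.

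**2. Week labels.** The example counts back from the termination day and the rule from the last diary day. With termination on day L+1, the nearest week end differs for L = 10, 17, …, 94, which is 13 values. For instance, L = 24 is nearest to Day 21 (Week 3), while Day 25 is nearest to Day 28 (Week 4). The Week 14 rule overrides L = 87 and L = 94, leaving 11 (L = 10, 17, …, 80).

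**3. Can an observed week become missing?** Entries on Days 2–15 and Day 23 only: literal Week 3 (Days 16–22) holds 0 values, and Days 17–23 hold 1. With no gaps in the diary, checking every L from 2 to 106, a week is lost only at L = 2, where the window ends on Day 1 (taking Day 7 as the nearest week end). Otherwise at least 7 days without an entry must precede the last one.

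**4. Size for one subject.** With all entries present, the last weekly mean changes by (score on day L − score on day L−7)/7. The maximum is 10/7 = 1.43 points. With independent days, the SD of the change is SD_day × √2/7:

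- SD_day 0.8: 0.16
- SD_day 1.2: 0.24
- wider range, SD_day 0.5 to 2: 0.10 to 0.40

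**5. Size for the arm difference.** Assume 15–25% of 235 per arm fall under the rule (35 to 59 subjects), and let the change pass one-for-one into Week 14. The SD of the change in the arm difference is SD_shift × √n/235 × √2:

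- 0.16 × √35/235 × √2 ≈ 0.006
- 0.24 × √59/235 × √2 ≈ 0.011
- 0.40 × √59/235 × √2 ≈ 0.019 (the widest SD)

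This is the random part only. If final entries run d points higher on average than those 7 days earlier, each affected subject moves by d/7. With 15% affected in one arm and 25% in the other, the arm difference moves by 0.10 × d/7 = 0.014d.

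**The case against.** The strongest reply is that this is loose wording whose intent can be recovered. The example, the relaxed Week 14 rule and most of Appendix C point to a week ending on the last diary day, and the rule treats both arms alike. Three stronger readings that a reader might infer do not hold.

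- **That the rule mis-sets the primary Week 14 value for subjects who stop just short of the end.** For a last entry on Day 95 the literal rule gives Days 88–94, but the Week 14 rule and Appendix C both give Days 89–95. For last entries on Days 85–98 the fault is a conflict between rules, not a certain loss.
- **That the rule flatly contradicts its own example.** That needs the last entry to be on Day 23. The day-before-visit pattern is stated for the Day 99 visit in 8.2.1 and for most completers in 12.3, not for early terminations.
- **That observed weeks will routinely be lost.** This needs a gap of 7 or more days before one last entry, or a single entry on Day 2. Protocol 12.2.6 has sites contact patients after two missed entries, and the documents give no frequency for longer gaps.

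The Day 106 evidence is also mixed: the late row of Appendix C agrees with the literal rule, against the Day 106 sentence.

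The core point stands. The sentence excludes the last entry on its face, and for diaries ending before Day 85 no other rule corrects it.

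**Conclusion.** The rule is inconsistent with the rest of SAP 8.2.1 and should be corrected. As worded it drops the last diary entry for every subject it governs. That conflicts with the Week 14 rule, with Appendix C apart from the 106+ row, with the Day 106 sentence and, if the last entry was the day before termination, with the worked example.

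Its practical reach is the weekly scores before Week 14 that serve as imputation covariates, plus the Week 14 value of subjects with no final visit whose diary runs past Day 98.

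The effect on the treatment difference is probably very small. A random change of about 0.01 NRS points or less follows from an assumed day-to-day SD of 0.8–1.2 and 15–25% affected, and about 0.02 at an SD of 2. Both figures assume the change carries fully into Week 14. That overstates it for subjects whose Week 14 is imputed, because the shifted weeks are then only predictors. The documents do not support a claim of material bias. The reason to act is that the derivation should have a single reading.

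**What to change.** Make three edits in the SAP together, before database lock:

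1. In 8.2.1, replace the averaging sentence: *the week whose nominal end day lies nearest to the last diary day takes the 7 days that end on, and include, that last diary day.*
2. Restate the example with both dates: *last diary entry Day 23 (ET visit Day 24): Week 3 = Days 17–23.*
3. Choose one upper limit and apply it in both places. The new sentence gives Days 100–106 for a last entry on Day 106, which fits the Day 106 sentence but not the Appendix C late row (Days 99–105). Changing the first sentence alone would leave that conflict open.

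The cost is one sentence, one example and one table row. It needs no new data and does not affect patients.

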8.2.2 Average Daily Sleep Quality Score

The average daily sleep quality score will be obtained in the same manner as the average daily pain score, via electronic Interactive Response Technology (IRT) system. Derivation of the weekly average sleep quality scores and censoring of data will be treated the same as the weekly average pain scores described in [Section 8.2.1](#), using the same windows based on the date of collection. It should be noted that the sleep prompt asks about the prior night's sleep; thus, subjects report their sleep starting the first night that they take randomized drug through the night

between day 97-98, if their final visit is day 99. As with pain, negative changes will denote improvement in sleep quality and larger negative values will denote greater improvement.

8.2.3 Patient Global Impression of Change (PGIC)

PGIC is a question completed by the subject at Weeks 2, 6, 10, and 14. The subject will rate the change in their overall fibromyalgia symptoms on a 1-7 Likert scale, where 1 is “Very Much Improved” and 2 is “Much Improved”. Scores of 1 and 2 will be considered PGIC responders, and all other scores will be considered non-responders for that visit. The proportion of responders in each treatment arm will be analyzed. Any missing PGIC score will be considered a non-responder for that visit.

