- Assess occurrence of adverse events
- Have the patient complete all PROs: (Telephone visit exception – all PROs should be mailed ahead of the visit and returned to the clinic after completion via courier):
 - a. PGIC
 - b. FIQR
 - c. Clinic administered assessment of pain by both 24-hour and weekly recall using 11-point (0-10) NRS scale
 - d. PROMIS scales for sleep disturbance and fatigue
 - e. CSFQ-14 female or male version, as appropriate
- Brief physical examination, including vital signs, weight (Telephone visit exception – brief physical exam, vital signs, and weight are not required)
- Inspection of the oral cavity. Ensure that this exam includes the sublingual area and that any abnormalities are carefully described on the oral exam source document. (Telephone visit exception – visual exam of the oral cavity is not required – but in addition to standard inquiry about AEs, site staff will inquire specifically if there have

been any changes or problems in the oral cavity. Patients reporting any concerning lesion description or painful processes in the oral cavity possibly related to study drug exposure should be strongly urged to come into the clinic for an unscheduled visit for oral cavity exam). In circumstances in which, due to the COVID-19 pandemic it is not possible for the patient to return to the clinic for the Unscheduled Visit exam, a clinician certified by the Sponsor to conduct oral cavity examination should contact the patient by phone and obtain greater history and description of the oral cavity AE by patient, potentially augmented with images of oral cavity taken by the patient and sent to the site for the examining clinician to *textually* document in the oral exam source document.)

- Obtain blood for clinical laboratory tests (Telephone visit exception – laboratory tests are not required).
- Perform in-clinic urine pregnancy test (for women of child-bearing potential) (Telephone visit exception – urine pregnancy test will be performed at home by patient for women of child-bearing potential).

Once these assessments have been completed, the patient may be discharged from the study, provided that there is no need for additional follow-up to continue to monitor an adverse event or other condition.

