13.4.4. Secondary Efficacy Analyses

Secondary efficacy analyses will be based on the ITT population only. For PGIC, patients with a “very much improved” or “much improved” response at the Week 14 endpoint will be considered responders. Patients with results in any other category or who discontinue early will be considered non-responders. PGIC responder status (yes/no) will be analysed using logistic regression with treatment and site as categorical effects. In addition, odds ratios and corresponding 95% confidence intervals will be presented.

Analysis of continuous secondary endpoints and adjustments for missing data will be described in detail in the SAP. Significance tests of treatment differences will be tested at the two-sided 0.05 level and corresponding 95% confidence intervals will be calculated.

To adjust for multiplicity and to control for overall type I error, a sequential test procedure will be applied to the efficacy endpoints. If the primary analysis produces a result that is statistically significant at the 0.05 level, a significance level of 0.05 will be used for comparing the secondary endpoints in an ordered fashion. If the analysis for a secondary endpoint does not produce a statistically significant result at the 0.05 level, then the remaining secondary endpoint analyses will automatically be considered non-significant regardless of the p-value produced. The order in which the secondary endpoints are to be tested will be specified in the SAP.

No other adjustments for multiplicity will be made and other p-values displayed in the output will be considered for descriptive summary purposes only and will not be used for formal inference. Full details regarding the statistical analyses for the listed endpoints, including graphical presentations, can be found in the SAP.

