8.1.2 Data Handling for Subjects Who Withdraw/Drop Out from the Study

Subjects who withdraw/drop out from the study will have the early termination (ET) data collected at their ET visit included in the analysis at the closest visit (Week 2, 6, 10, 14), using midpoints between visits to window the early termination. If this results in two records for a given visit, then the one closest to the targeted date will be used.

For example, a subject with valid Week 10 clinic assessment collected on Day 72 that has early termination data collected on Day 79, would have the early termination data mapped to Week 10; however, since Day 72 data is present and closer to the target date, it would be analyzed and the Day 79 data would be excluded. A subject without valid Week 10 data who early terminates on Day 79 would have the Day 79 data analyzed with the Week 10 data.

Subjects who provide 14 weeks of diary pain data will be analyzed as completers for purposes of the primary analysis, even if for some reason they are unable to attend a Week 14 final study visit. As a specific example, a subject who successfully provides 14 weeks of diary data as described in [Section 8.2.1](#), but who is unable to attend a final study visit during the required time window because of travel or other circumstances, would be analyzed as a completer for purposes of the primary endpoint, but would be missing non-diary based secondary outcome measures at

the Week 14 endpoint. For safety data, the last observation available will be summarized in addition to the presentation above (grouping ET visits with the closest planned visit); this will combine the ET visit data with the completers' Week 14 data, regardless of when the ET occurred.

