3. For subjects that discontinue for LOE or AEs, an iterative process will be applied moving through each week. The complete MAR dataset from step 2 above will be used and augmented with subjects missing for the week being imputed at that stage. The non-missing values for the week in question will temporarily be set to the subjects corresponding baseline value, so the data from LOE and AE subjects are imputed for that week drawing from the baseline distribution. This will proceed from Week 1 to Week 14 with the imputed complete dataset for a week serving as the basis for the subsequent week. Covariates at each stage will include the values for the prior weeks (observed, MAR imputed in steps 1& 2, or imputed previously in this step) and site.

The above process will be done independently for the subjects included in the interim analysis and those not in the interim.

Daily sleep diary data will be handled in an identical manner to the pain scores.

Continuous outcomes included in the list of key secondary outcomes that are collected in-clinic will be handled as above, minus the step of creating weekly averages of daily values and with steps being done by visit instead of week.

Subjects with missing PGIC at a given visit will be considered non-responders at that visit for the purposes of treatment comparisons and efficacy claims; additional tabulations will summarize the number and percentage in each category out of non-missing values as well as a count of the missing values.

No missing safety data will be imputed.

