10.2 Secondary Efficacy Analyses

Secondary efficacy analyses will be based on the ITT population only.

Continuous Endpoints

For the purposes of possible label claims and reported p-values entered into the multiplicity algorithm, an approach identical to the primary analysis will be used for all continuous outcomes. See [Section 8.1.3](#) for the imputation algorithm and [Section 10.1.2](#) for the analysis approach.

Outcomes using these analyses will include:

- Change from baseline in the FIQR symptoms domain score
- Change from baseline in the FIQR function domain score
- Change from baseline in the PROMIS score for sleep disturbance
- Change from baseline in the PROMIS score for fatigue
- Change from baseline in the weekly average of the daily diary assessment of sleep quality.

For each, all time points will be summarized, but the primary time point of interest is Week 14. Time points other than Week 14 are considered exploratory. The estimand for each is identical to the primary, substituting for the endpoint in question.

For the sleep quality assessment collected via a daily subject diary, the baseline score and the weekly scores for each subject will be calculated as the weekly average score based on the mean of the scores recorded for that study week ([Section 8.2.2](#)).

This will be repeated on the outcomes above, but using observed data only without imputation.

Categorical Endpoints

A categorical analysis of PGIC will be performed using a logistic regression model for each week with effects for treatment and investigative site. If the model does not converge, site will be removed from the model. Subjects with results of “very much improved” or “much improved” (defined as responders) will be compared to all other categories (defined as non-responders). Subjects with missing data will be considered non-responders. In addition, odds ratios and corresponding 95% CI intervals for being “very much improved” or “much improved” versus all other categories will be presented. A summary of frequency counts for PGIC responses for each time point will be presented; Week 14 is of primary interest and all other time points are considered exploratory.

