13. CHANGES FROM PLANNED ANALYSIS

The protocol inadvertently omitted the in-clinic pain assessments from the list of exploratory endpoints; it was added to this SAP.

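### The SAP can count a late discontinuer as a Week 14 PGIC responder, against the protocol's rule and without declaring the change; one Appendix C row also needs correcting

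*SAP*

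**What the plan says.** **PGIC.** Protocol 13.4.4 defines responders by the two best ratings at Week 14 and adds: "Patients with results in any other category or who discontinue early will be considered non-responders". The SAP states its rule three times, and none of the three mentions discontinuation:

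- 8.1.3: "Subjects with missing PGIC at a given visit will be considered non-responders at that visit"
- 8.2.3: "Any missing PGIC score will be considered a non-responder for that visit"
- 10.2: "Subjects with missing data will be considered non-responders"

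At an early termination (ET) visit, protocol 11.5.2 tells the site: "Have the patient complete all PROs". PGIC is the first instrument on that list. SAP 8.1.2 says that ET data are "included in the analysis at the closest visit (Week 2, 6, 10, 14), using midpoints between visits to window the early termination". Its worked example shows that they then count as visit data: a subject without a valid Week 10 assessment "who early terminates on Day 79 would have the Day 79 data analyzed with the Week 10 data". SAP 13 declares a single departure from the protocol: "The protocol inadvertently omitted the in-clinic pain assessments from the list of exploratory endpoints".

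**Diary.** SAP 8.2.1 builds the Week 14 mean from an anchor day and the 6 days before it, and Appendix C tabulates the result. For a visit on Day 93 with last diary Day 92, the table uses Days 85-92. A later paragraph of 8.2.1 assigns the diaries of early withdrawals to the week whose nominal end is nearest.

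**The concern.** A patient who stops late, attends the ET visit and rates 1 or 2 has a non-missing PGIC score that SAP 8.1.2 places at Week 14. The SAP then counts a responder where the protocol counts a non-responder. PGIC opens the fixed testing sequence (SAP 8.1.1.2), so if it fails, the other five key secondary endpoints fail with it. Its responder definition should match the protocol or be declared as changed before unblinding.

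The diary text feeds the primary endpoint. One table row contradicts the rule that it illustrates, and the order of the rules for late withdrawals has to be pieced together from several sentences.

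**Working it through.** **1. Which ET visits map to Week 14**

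Inputs: Week 10 target Day 71 (protocol 11.4); Week 14 target Day 99, window -4/+7 (protocol 11.5.1).

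- Check against the SAP's example: Day 79 is 8 days from Day 71 and 20 from Day 99, so Week 10. This reproduces 8.1.2.
- Midpoint: (71 + 99)/2 = 85. Day 85 is 14 days from each target, and the SAP has no rule for the tie.
- Day 86: 86 - 71 = 15 and 99 - 86 = 13, so Week 14.
- The Visit 6 window opens on 99 - 4 = Day 95. The clearest conflict is therefore Days 86-94, which is 9 days.
- An ET visit up to Day 84 maps to Week 10 or earlier. Week 14 PGIC is then missing, and both documents give a non-responder.

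**2. How many patients could change status**

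The documents give 235 per arm. Dropout, ET attendance and the responder share among late leavers are not given, so all three are assumptions, as is an even spread of ET visits over 98 days.

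Patients per arm = 235 x dropout x 9/98 x attendance x share rating 1 or 2.

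| Assumptions | Low | High |
|---|---|---|
| A: dropout 15-25%, attendance 50-100%, share 10-33% | 3.24 x 0.5 x 0.10 = 0.16 | 5.40 x 1 x 1/3 = 1.80 |
| B: dropout 10-30%, attendance 100%, share 20-50% | 2.16 x 0.20 = 0.43 | 6.47 x 0.50 = 3.24 |

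Across both sets this is 0.16/235 to 3.24/235, or 0.07 to 1.38 percentage points per arm. One patient is 1/235 = 0.43 points.

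The treatment difference does not move if the arms are alike. With one arm at the high end and the other at the low end it moves by (1.80 - 0.16)/235 = 0.70 points in set A and (3.24 - 0.43)/235 = 1.19 points in set B. The standard error, sqrt(2p(1-p)/235), is 3.69 points at p = 20% and 4.52 at p = 40%. The shifts are then 0.15-0.19 SE (A) and 0.26-0.32 SE (B).

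Illustration at the threshold (pooled two-proportion z-test, no site term, two-sided 0.05 as in the protocol because the SAP's level is redacted): 79/235 against 59/235 gives p = 0.043, and 78/235 against 59/235 gives p = 0.054.

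**3. Appendix C**

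With last diary day L, the rule is Days L-6 to L. Of the 15 rows with a single last diary day, 14 reproduce. For L = 92 the rule gives Days 86-92 (7 days); the table has 92 - 85 + 1 = 8 days. The extra day has weight 1/8, so it moves that patient's Week 14 mean by 0.125 for each point by which Day 85 differs from the mean of Days 86-92.

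Two other entries disagree with the text. A comment gives the Week 14 window as 4 days either side of Day 99, against -4/+7 in the protocol and 8.2.1. The row for diaries running to Day 106 or later stops at Day 105, while 8.2.1 makes Day 106 the last day allowed.

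**4. Order of the diary rules**

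Nominal week ends are Days 84, 91 and 98. Taken alone, the nearest-week-end rule gives:

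- Anchor = last diary day L: L of 85-87 goes to Week 12, 88-94 to Week 13, 95 onward to Week 14.
- Anchor = termination day, taken as L+1: L of 85-86 goes to Week 12, 87-93 to Week 13, 94 onward to Week 14.

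The text names the last diary day as anchor. Its example (termination on Day 24, Days 17-23 used) fits the termination day. The COVID-19 relaxation in 8.2.1 and Appendix C instead give an observed Week 14 whenever there is a score on or after Day 85.

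With 15-25% dropout spread evenly, 235 x 0.15 x 9/98 = 3.24 to 235 x 0.25 x 10/98 = 5.99 patients per arm would have a last diary day in the affected 9 or 10 days.

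**The case against.** **The protocol defers to the SAP for detail.** It does, but in 13.4.4 the missing-data adjustments left to the SAP are tied to the continuous endpoints. PGIC is analysed as a binary outcome, and a rating given at an ET visit is not missing. Leaving details to the SAP does not reverse a responder definition that the protocol states outright.

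**Using the observed ET rating is a defensible choice.** It is, and the sponsor may keep it. What is missing is the declaration.

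**The diary order is already settled.** This largely stands. SAP 8.2.1 sends on only subjects without data from Day 85, Appendix C repeats that test and derives the other weeks from the Week 14 interval, and the early-withdrawal paragraph itself gives a Week 14 value to lost-to-follow-up diaries that reach that week. A reader might infer that the primary endpoint is undefined for late withdrawals. The documents do not support that. What remains is that the early-withdrawal paragraph accepts anchors up to Day 106 without saying that it yields, and that the visit-anchored rule and the search back from Day 98 are not ranked. For a Day 106 visit they give Days 99-105 and Days 92-98.

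**The Appendix C slip is one digit.** True. The text gives the rule and the neighbouring rows follow it. It is minor, and the digit should be confirmed against the signed copy.

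**The sizes are soft.** This stands as well. Protocol 11.5.2 encourages an ET visit even after a lapse in dosing, so ET dates need not be evenly spread.

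**Conclusion.** The PGIC rule is wrong as written: protocol and SAP classify the same late discontinuer differently on the first key secondary endpoint, and SAP 13 does not say so. The conflict is confined to ET visits from Day 86 on and is clearest for Days 86-94.

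The likely effect is small, roughly 0.2 to 3 patients per arm. That range rests entirely on assumed dropout, attendance and responder shares, so it is an illustration and not a limit. It matters mainly if the PGIC result falls close to the significance threshold.

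A reader might infer that the SAP rule favours TNX-102 SL. The documents give no dropout or ET ratings by arm, so the direction is unknown.

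The Appendix C row is also wrong as written, but minor. The order of the diary rules needs a clarity edit only.

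**What to change.** Before unblinding:

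1. **PGIC.** State in SAP 8.1.3, 8.2.3 and 10.2 that early discontinuers are Week 14 non-responders whatever their ET rating. Define early discontinuer for this purpose, for example by recorded study-completion status, so that ET visits on Days 95-98, inside the Visit 6 window, are covered. If the SAP rule is kept instead, declare it in SAP 13, run the protocol rule as a sensitivity analysis, and settle the Day 85 tie.
2. **Appendix C.** Change the row for last diary Day 92 to Days 86-92. Align the window comment with -4/+7, and the row for Day 106 and later with Day 106 as the last allowable day.
3. **SAP 8.2.1.** State that the nearest-week-end rule applies only to subjects with no diary score on or after Day 85. Rank the visit-anchored rule and the search back from Day 98. Say whether the early-withdrawal anchor is the last diary day or the termination day.

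The cost is SAP wording and one PGIC derivation flag, plus one extra logistic regression if the SAP rule is kept. No new data are needed.
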